3.3.2 Exclusion Criteria

1. Patients who because of age, general medical or psychiatric condition, or physiologic status cannot give valid informed consent.
2. Concurrent treatment with any dose of systemic glucocorticoids within 7 days prior to C1D1.
3. History of adrenal insufficiency requiring use of systemic glucocorticoid replacement.
4. History of Cushing's disease or Cushing's syndrome.
5. Any condition that, in the opinion of the Principal Investigator, would impair the patient's ability to comply with study procedures.
6. Contra-indication to MRI (e.g. pacemaker placement, severe claustrophobia) (applicable only for patients scheduled for PET/MRI).

3.4 Study Timeline

3.4.1 Primary Completion

The estimated study period is approximately 36 months from the date of first patient enrolled.

3.4.2 Study Termination

The principal investigator reserves the right to terminate the study at any time.

Termination of the study will be considered in the event of any safety concerns arising at any time during the performance of the study.

If it becomes necessary to consider termination of the study after dosing has begun, dosing may be suspended pending discussion between the investigators and the DSMC.

4 Investigational Medicinal Product

¹¹C-YJH08 is a radiopharmaceutical that will be produced under cGMP in the Department of Radiology and Biomedical Imaging Radiopharmaceutical Facility. The radiopharmaceutical will be prepared in the same facility in which the injection and imaging will take place, the China Basin Imaging Center.

¹¹C-YJH08 will be administered on an outpatient basis. It will be administered intravenously prior to PET imaging. The injected dose will be approximately 20 mCi. Between 10-60 minutes following ¹¹C-YJH08 injection, one or more whole body CT (PET/CT) or MRI (PET/MR) scans will be used for attenuation correction and anatomic localization of ¹¹C-YJH08 and SUV calculation.

¹¹C-YJH08 Injection is the IMP in this study.

5 Study Procedures and Schedules of Events

5.1 Participant Registration

A written, signed, informed consent form (ICF) and a Health Insurance Portability and Accountability Act (HIPAA) authorization must be obtained before any study-specific assessments are initiated. A copy of the signed ICF will be given to the subject and a copy will be filed in the medical record. The original will be kept on file with the study records.

All participants consented to the study will be registered in OnCore®, the UCSF Helen Diller Family Comprehensive Cancer Center Clinical Trial Management System (CTMS). The system is password protected and meets HIPAA requirements.

A list of study subjects will be completed and will include each subject's study number and initials. The investigator must also maintain a separate log of all the subjects screened for participation in the study but who will not participate, the reasons for their exclusion or non-participation, their initials, and the date on which the subject was excluded.

5.2 Schedule of Procedures and Assessments

5.2.1 Screening Assessments

The screening procedures and assessments must be completed within 28 days of baseline PET (PET/CT or PET/MR) scan except for staging scans which need to be completed 12 weeks prior to baseline PET. All screening procedures may be performed on the same day as baseline PET, provided screening and eligibility confirmation is completed and verified by Principal Investigator prior to initiation of PET.

- Baseline conditions
- Vital signs including heart rate and blood pressure

- Concomitant medication review
- AE assessment
- Demographic information (e.g. age, race, height, weight, and body mass index)
- Staging scans - cross-sectional imaging of the chest/abdomen/pelvis (CT or MRI; with IV contrast if medically permissible) within 12 weeks of baseline ^{11}C -YJH08 PET.
- ECOG or Karnofsky Performance status
- Laboratory procedures
 - Serum creatinine
 - Total bilirubin
 - Aspartate aminotransferase (AST)
 - Alanine aminotransferase (ALT)
 - Complete blood count + differential
 - Prostate-specific antigen (PSA)
 - Serum testosterone. Result may be pending at the time of completion of baseline PET provided documentation of ongoing LHRH analog treatment is available (see eligibility criteria above)

5.2.2 Day 1, Baseline ^{11}C -YJH08 PET

For cohort A (dosimetry calculation), multiple time points (up to 5 time points) will be obtained. Imaging will begin immediately after injection of radiotracer and continue up to ~90 minutes after injection of the radiopharmaceutical. From the 90 minutes of data collected, up to 5 time points will be selected, and reconstructions will be performed. For Cohorts B and C, one to two time point whole body PET/CT or PET/MR scans will be performed extending from the patient's vertex through the thighs. Uptake time will be based on the initial results of Cohort A, though may be adjusted based on the data obtain during the study.

The following procedures and assessments will be performed:

- Imaging will begin immediately after injection of ^{11}C -YJH08.
 - Cohort A imaging will be performed up to 5 time points
 - Cohorts B and C whole body PET/CT (or PET/MR) will be performed one or two times.
- Vital signs including heart rate and blood pressure will be collected at screening, before and after administration of ^{11}C -YJH08 injection, then at 60 minutes (+/- 15 min), and 2 hours (+/- 30 min), following ^{11}C -YJH08 injection.
- Safety monitoring will include adverse event assessment during screening, 60 minutes (+/- 15 min), 2 hours (+/- 30 min) and 24 hours (+/- 4 hours) following ^{11}C -YJH08 injection. No iodinated contrast or gadolinium will be administered.
- Serum creatinine, total bilirubin, AST, ALT, and CBC + diff will be performed at screening and at 24 hours (+/- 4 hours) following ^{11}C -YJH08 injection.
- EKG/ECG will be performed prior to ^{11}C -YJH08 injection (up to 4 hours prior) and at 2 hours (+/- 30 min) following ^{11}C -YJH08 injection.

No formal report of the findings from imaging studies will be created. Each scan will be reviewed by a board-certified nuclear medicine physician and radiologist within two working days of the

completion of the study. If any unexpected findings are visualized, these will be reported to the treating health care provider, who will then contact the patient if additional work-up needs to be performed. The reviewing nuclear medicine physician will be required to sign a written form indicating that they have reviewed the scan results and communicated any clinically pertinent findings to the treating physician within two business days of scan completion.

Baseline Tumor Biopsy (Optional)

Patients will undergo optional metastatic tumor biopsy within 14 days following completion of baseline PET scan. The biopsy sample will be analyzed for protein expression of GR by IHC and RNA-seq for application of GR transcriptional signature when sufficient tumor content is present. Soft tissue, PET-avid lesions will be prioritized for biopsy.

5.2.3 OPTIONAL ^{11}C -YJH08 PET at Progression (Cohorts B and C)

Patients will undergo optional repeat ^{11}C -YJH08 PET at the time of progression by PCWG3 criteria for Cohort B and RECIST 1.1 criteria for Cohort C. Patients who underwent PET/CT at baseline should have same imaging modality performed during follow-up, and likewise patients who underwent PET/MR at baseline should have same imaging modality performed during follow up.

- Vital Signs
- Concomitant medication review

Period/ Procedure	Screening (Day -28 thru C1D1)	Cycle 1, Day 1 (Baseline PET)	Disease Progression (Cohort B and C)
Study / Investigational Product Administration			
¹¹ C-YJH08 PET		X	X
Administrative Procedures			
Informed consent	X		
Clinical Assessments			
Baseline conditions	X		
Vital signs ¹	X	X	X
Concomitant medications	X		X
AE assessment ²	X	X	
Demographics	X		
Performance status	X		
Laboratory Assessments			
Serum creatinine, total bilirubin, AST, ALT, CBC + diff ³	X	X	
PSA, Serum Testosterone	X		
Imaging Procedures			
Staging scans (CT or MRI)	X		
ECG/EKG		X ⁴	
Tissue Collection/ Biopsy			
Tumor biopsy (optional) ⁵		X	

¹ Vital signs (blood pressure, heart rate) will be collected at screening, before and after administration of ¹¹C-YJH08 injection, then at 60 minutes (+/- 15 min), and 2 hours (+/- 30 min) following ¹¹C-YJH08 injection.

² Safety monitoring will include adverse event assessment at screening, 60 minutes (+/- 15 min), 2 hours (+/- 30 min) and 24 hours (+/- 4 hours) following ¹¹C-YJH08 injection.

³ Serum creatinine, total bilirubin, AST, ALT, and CBC + diff will be performed at screening and at 24 hours (+/- 4 hours) following ¹¹C-YJH08 injection.

⁴ EKG will be performed prior to ¹¹C-YJH08 injection and at 2 hours (+/- 30 min) following ¹¹C-YJH08 injection.

⁵ Metastatic tumor biopsy is optional. Tumor biopsy should be performed within 14 days following baseline PET. Soft tissue, PET-avid lesions should be prioritized for biopsy whenever feasible.

Supportive Care

Subjects will receive full supportive care as medically indicated.

The Principal Investigator or designee will be present during the administration and monitoring period. Any events occurring during or subsequent to the administration of IMP will be addressed as required by the monitoring nurse and/or physician as deemed appropriate.

6 Reporting and Documentation of Results

6.1 Evaluation of Safety

Analyses will be performed for all patients having received at least one dose of IMP. The study will use the CTCAE v5.0 criteria for reporting of non-hematologic adverse events and modified criteria for hematologic adverse events.

6.2 Definitions of Adverse Events

6.2.1 Adverse Event

An adverse event (also known as an adverse experience) is defined as any untoward medical occurrence associated with the use of a drug in humans, whether or not considered drug related. More specifically, an adverse event (can be any unfavorable and unintended sign (e.g., an abnormal laboratory finding), symptom, or disease temporally associated with the use of a drug, without any judgment about causality. An adverse event can arise from any use of the drug (e.g., off-label use, use in combination with another drug) and from any route of administration, formulation, or dose, including an overdose.

Laboratory test value abnormalities will not be recorded as AEs unless they are designated as clinically significant, defined as any one of the following: symptomatic, requiring treatment, resulting in dose modification or delay or premature study withdrawal, or placing the subject at risk for other toxicity in the judgment of the treating investigator.

6.2.2 Adverse Reaction

An adverse reaction is defined as any adverse event caused by the use of a drug. Adverse reactions are a subset of all suspected adverse reactions for which there is reason to conclude that the drug caused the event.

6.2.3 Suspected Adverse Reaction

A suspected adverse reaction is defined as any adverse event for which there is a reasonable possibility that the drug caused the adverse event. For the purposes of IND safety reporting, "reasonable possibility" indicates that there is evidence to suggest a causal relationship between the drug and the adverse event. A suspected adverse reaction implies a lesser degree of certainty about causality than an adverse reaction.

6.2.4 Unexpected

An adverse event or suspected adverse reaction is considered *unexpected* if it is not listed in the investigator brochure or package insert(s), or is not listed at the specificity or severity that has been observed, or, if an investigator brochure is not required or available, is not consistent with the risk information described in the general investigational plan or elsewhere in the current application.

“Unexpected,” as used in this definition, also refers to adverse events or suspected adverse reactions that are mentioned in the investigator brochure as occurring with a class of drugs or as anticipated from the pharmacological properties of the drug, but are not specifically mentioned as occurring with the particular drug under investigation.

Adverse events that would be anticipated to occur as part of the disease process are considered *unexpected* for the purposes of reporting because they would not be listed in the investigator brochure. For example, a certain number of non-acute deaths in a cancer trial would be anticipated as an outcome of the underlying disease, but such deaths would generally not be listed as a suspected adverse reaction in the investigator brochure.

Some adverse events are listed in the Investigator Brochure as occurring with the same class of drugs, or as anticipated from the pharmacological properties of the drug, even though they have not been observed with the drug under investigation. Such events would be considered *unexpected* until they have been observed with the drug under investigation. For example, although angioedema is anticipated to occur in some patients exposed to drugs in the ACE inhibitor class and angioedema would be described in the investigator brochure as a class effect, the first case of angioedema observed with the drug under investigation should be considered *unexpected* for reporting purposes.

6.2.5 Serious

An adverse event or suspected adverse reaction is considered *serious* if, in the view of either the investigator or sponsor, it results in any of the following outcomes:

- Death
- Life-threatening adverse event
- Inpatient hospitalization or prolongation of existing hospitalization
- A persistent or significant incapacity or substantial disruption of the ability to conduct normal life function
- Congenital anomaly/birth defect
- Cancer

Important medical events that may not result in death, are life-threatening, or require hospitalization may be considered serious when, based upon appropriate medical judgment, they may jeopardize the patient or subject and may require medical or surgical intervention to prevent one of the outcomes listed in this definition. Examples of such medical events include allergic bronchospasm requiring intensive treatment in an emergency room or at home, blood dyscrasias or convulsions that do not result in inpatient hospitalization, or the development of drug dependency or drug abuse.

6.2.6 Serious

An adverse event or suspected adverse reaction is considered *life-threatening* if, in the view of either the investigator or sponsor, its occurrence places the patient or subject at immediate risk of death. It does not include an adverse event or suspected adverse reaction that, had it occurred in a more severe form, might have caused death.

6.3 Recording of an Adverse Event

All grade 3 and above adverse events will be entered into OnCore®, whether or not the event is believed to be associated with use of the IMP. Data about these events and their severity will be recorded using the NCI CTCAE v5.0.

The Investigator will assign attribution of the possible association of the event with use of the investigational drug, and this information will be entered into OnCore® using the classification system listed below:

Relationship	Attribution	Description
Unrelated to investigational drug/intervention	Unrelated	The AE is clearly NOT related to the intervention
	Unlikely	The AE is doubtfully related to the intervention
Related to investigational drug/intervention	Possible	The AE may be related to the intervention
	Probable	The AE is likely related to the intervention
	Definite	The AE is clearly related to the intervention

Signs or symptoms reported as adverse events will be graded and recorded by the Investigator according to the CTCAE. When specific adverse events are not listed in the CTCAE they will be graded by the Investigator as *none, mild, moderate* or *severe* according to the following grades and definitions:

- Grade 0 No AE (or within normal limits)
- Grade 1 Mild; asymptomatic or mild symptoms; clinical or diagnostic observations only; intervention not indicated
- Grade 2 Moderate; minimal, local, or noninvasive intervention (e.g., packing, cautery) indicated; limiting age-appropriate instrumental activities of daily living (ADL)
- Grade 3: Severe or medically significant but not immediately life-threatening; hospitalization or prolongation of hospitalization indicated; disabling; limiting self- care ADL
- Grade 4: Life-threatening consequences; urgent intervention indicated
- Grade 5: Death related to AE

6.4 Follow-up of Adverse Events

All adverse events will be followed with appropriate medical management until resolved. Patients removed from study for unacceptable adverse events will be followed until resolution or stabilization of the adverse event. For selected adverse events for which administration of the investigational drug was stopped, a re-challenge of the subject with the investigational drug may be conducted if considered both safe and ethical by the Investigator.

6.5 Adverse Events Monitoring

All adverse events, whether or not unexpected, and whether or not considered to be associated with the use of the IMP, will be entered into OnCore®, as noted above.

The Investigator will assess all adverse events and determine reportability requirements to the UCSF Data and Safety Monitoring Committee (DSMC) and UCSF's Institutional Review Board; and, when the study is conducted under an Investigational New Drug Application (IND), to the Food and Drug Administration (FDA) if it meets the FDA reporting criteria.

All adverse events entered into OnCore® will be reviewed by the Helen Diller Family Comprehensive Cancer Center Site Committee on a weekly basis. The Site Committee will

review and discuss at each weekly meeting the selected toxicity, the toxicity grade, and the attribution of relationship of the adverse event to the administration of the IMP(s).

In addition, all adverse events and suspected adverse reactions considered “serious,” entered into OnCore® will be reviewed and monitored by the Data and Safety Monitoring Committee on an ongoing basis, discussed at DSMC meetings which take place every six (6) weeks. For a detailed description of the Data and Safety Monitoring Plan.

6.6 Expedited Reporting

6.6.1 Reporting to the Data and Safety Monitoring Committee

If a death occurs during the treatment phase of the study or within 30 days after the last administration of the IMP(s) and it is determined to be related either to the IMP(s) or to a study procedure, the Investigator or his/her designee must notify the DSMC Chair (or qualified alternate) within 1 business day of knowledge of the event. The contact may be by phone or e-mail.

6.6.2 Reporting to UCSF Institutional Review Board

The Principal Investigator must report events meeting the UCSF IRB definition of “Unanticipated Problem” (UP) within 10 business days of his/her awareness of the event.

6.6.3 Expedited Reporting to the Food and Drug Administration

The Sponsor-Investigator is responsible for determining whether or not the suspected adverse reaction meets the criteria for expedited reporting in accordance with Federal Regulations (21 CFR §312.32).

The Investigator must report in an IND safety report any suspected adverse reaction that is both serious and unexpected. The Sponsor-Investigator needs to ensure that the event meets all three definitions:

- Suspected adverse reaction
- Unexpected
- Serious

If the adverse event does not meet all three of the definitions, it should not be submitted as an expedited IND safety report.

The timeline for submitting an IND safety report to FDA is no later than **15 calendar days** after the Investigator determines that the suspected adverse reaction qualifies for reporting (21 CFR 312.32(c)(1)).

Any unexpected fatal or life-threatening suspected adverse reaction will be reported to FDA no later than **7 calendar days** after the Investigator’s initial receipt of the information (21 CFR 312.32(c)(2)).

Any relevant additional information that pertains to a previously submitted IND safety report will be submitted to FDA as a Follow-up IND Safety Report without delay, as soon as the information is available (21 CFR 312.32(d)(2)).

7 Statistical Analysis

7.1 Imaging Analysis

A trained nuclear medicine physician will evaluate the reconstructed PET, CT or MRI, and fused PET/CT or PET/MR images using a PET volume computer-assisted reading software package. A positive lesion on PET will be defined as a focus of activity with at least 1.5 times higher SUV compared with mediastinal blood pool that is not attributable to other etiologies of tracer distribution (e.g. inflammation, excretion). A volume of interest (VOI) will be semiautomatically placed around each lesion, and the calculated maximum standard uptake value (SUV_{max}) will be recorded for each lesion, including lesions that are detected on standard scans but are not positive on PET. Adjusted SUV_{max} data will then be averaged across all lesions within a given patient ($SUV_{max-avg}$). In order to avoid clustering effects, analysis will be limited to the five largest osseous metastases and all visceral/soft tissue metastases.

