7.2 Determination of Sample Size

A convenience sample size of approximately 6 patients for Cohort A is selected to collect sufficient scan data to ensure adequate organ dosimetry and determination of the optimal uptake time following administration of ^{11}C -YJH08. Additional patients may be accrued as necessary to optimize imaging acquisition parameters prior to proceeding to Cohort B and C enrollment.

Success for Cohort A will be defined as technically successful injection of radiotracer with expected biodistribution and visualization of radiotracer uptake in the expected location of a metastasis based on conventional imaging in at least one patient. If no metastases are visualized despite varying uptake time and injected dose after 6 or more patients are enrolled in Cohort A, then accrual will not proceed to Cohorts B and C.

For patients enrolled in Cohorts B and C, a convenience sample size of 10 evaluable patients per cohort is chosen to provide preliminary estimates of sensitivity of lesion detection on PET compared to conventional imaging. We expect 20% inevaluable rate over the course of the study; we will recruit 12 patients in each cohort to achieve the target sample size.

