7.7.2 Primary Analysis

For Cohort A, Using as a cut-off to define a positive lesion on PET as a lesion with SUV at least 1.5 times higher than mediastinal blood pool, the sensitivity of ^{11}C -YJH08 PET will be descriptively reported on a lesion-per-lesion basis, using as reference standard staging scans including CT or MRI of the chest/abdomen/pelvis.

For Cohorts B and C, the median percent change from baseline, and range of SUV_{max} (across all metastatic lesions per patient) and $\text{SUV}_{\text{max-ave}}$ (in each study cohort) will be descriptively reported using mediastinal blood pool and normal organ as background uptake values. Wilcoxon signed rank test will be used to compare the follow up to baseline PET scan values at lesion level and patient level.

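### Section 7.1 does not keep the staging scans from the physician who calls PET lesions, although staging is the reference standard for Cohort A sensitivity

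*Combined protocol and SAP*

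**What the plan says.** Section 2.2 makes sensitivity of metastatic lesion detection the Cohort A primary endpoint. Section 7.7.2 says that it "will be descriptively reported on a lesion-per-lesion basis", "using as reference standard staging scans including CT or MRI of the chest/abdomen/pelvis". No target value or test is attached.

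Section 7.1 describes the read: "A trained nuclear medicine physician will evaluate the reconstructed PET, CT or MRI, and fused PET/CT or PET/MR images". A PET-positive lesion is "a focus of activity with at least 1.5 times higher SUV compared with mediastinal blood pool" and one "that is not attributable to other etiologies of tracer distribution (e.g. inflammation, excretion"). A volume of interest (VOI) is placed semiautomatically on each lesion and SUVmax is recorded, "including lesions that are detected on standard scans but are not positive on PET".

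Section 7.2 counts Cohort A as a success if the injection works technically, the biodistribution is as expected, and there is "visualization of radiotracer uptake in the expected location of a metastasis based on conventional imaging in at least one patient". If no metastasis is seen after six or more patients, "then accrual will not proceed to Cohorts B and C". Section 7.6 adds an informal, qualitative look at the images at about six patients.

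No section says whether the staging scans or their report are available when PET positivity is called, or in what order the images are read.

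**The concern.** A sensitivity estimate describes the index test only if that test is called without knowledge of the reference result. Here the reference result is a list of sites on the staging CT or MRI. The physician who calls the PET also has to find and measure the staging lesions that the PET missed, so at some point that physician holds the list. Nothing stops this from happening before the calls are made.

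A reader who knows that a metastasis lies at a site is more likely to accept faint activity there as a focus, to place the VOI so that it takes in the hottest nearby voxels, and to attribute the uptake to tumour rather than to inflammation or excretion. All three push towards a positive call, so the expected bias is upward. At stake is whether the Cohort A figure shows what the tracer reveals by itself or what it shows to someone told where to look. Sections 2.1 and 7.2 also speak of sensitivity against conventional imaging in Cohorts B and C, so the same reading rule would carry forward.

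**Working it through.** The plan states no assumed sensitivity, reader error rate or power for Cohort A (7.2 calls it a convenience sample), so there is no figure to reproduce. The check sets the sections side by side and then shows a range.

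**Which CT or MRI is meant in 7.1.** Section 4 describes CT or MR scans used with the PET for attenuation correction and anatomical localisation. The wording of 7.1 most naturally refers to these companion scans. The reference standard is different: the staging CT or MRI of 5.2.1, done within 12 weeks of the baseline PET, with intravenous contrast where permissible. Section 5.2.2 says that no contrast is given at the PET visit. The quoted sentence alone therefore does not show that the reader sees the reference standard.

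**Where the reference map enters.** It enters through the SUVmax rule in 7.1, which covers standard-scan lesions that are not PET-positive. That step needs the staging map. A sequential read (call, then measure) satisfies the rule, and so does a read with staging open throughout. The text permits both.

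**Whether another section closes the gap.** The review in 5.2.2 by a nuclear medicine physician and radiologist is for unexpected findings and produces no formal report. It is not the endpoint read. No section provides for blinding to staging, a locked PET read or adjudication.

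**What the cut-off leaves open.** Let *s* be the sensitivity from a read without staging, and *f* the share of staging lesions left uncalled in that read that would be called once their location is known. Then

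reported sensitivity = *s* + (1 − *s*) × *f*

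A lesion whose recorded SUV stays below 1.5 times blood pool cannot be called positive by suggestion alone. So *f* cannot exceed the share of uncalled lesions whose SUV, in the VOI as placed, reaches the cut-off. If none does, *f* = 0 and there is no bias.

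**Illustration.** Both *s* and *f* are assumptions; the documents give neither.

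| *s* | *f* = 0.05 | *f* = 0.10 | *f* = 0.20 | *f* = 0.30 |
|---|---|---|---|---|
| 0.30 | 0.335 | 0.37 | 0.44 | 0.51 |
| 0.50 | 0.525 | 0.55 | 0.60 | 0.65 |
| 0.70 | 0.715 | 0.73 | 0.76 | 0.79 |

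For example, 0.50 + 0.50 × 0.10 = 0.55. Over this grid the shift runs from 0.30 × 0.05 = 1.5 percentage points to 0.70 × 0.30 = 21 points.

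**The case against.** **The reader may not have staging open.** A reader of 7.1 might infer that staging locations are in view when lesions are called. The documents do not say so. The label not positive on PET presupposes that a call has already been made, so a PET-first read fits the text. This stands: the defect is that the order is left open.

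**The cut-off does most of the work.** A threshold with a recorded SUVmax leaves less room for suggestion than a purely visual read. A lesion above the cut-off that an unprompted reader overlooks does have measured uptake, and calling it positive is not plainly an error. This also stands. It limits the size of the bias but does not remove the three judgements.

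**The decision to open Cohorts B and C.** A reader might infer that this decision is compromised too. If location-prompted reading gave a spurious call in a share *b* of patients with no real uptake, the chance of at least one success in six is 1 − (1 − *b*)^6: 26.5%, 46.9% and 73.8% for *b* = 0.05, 0.10 and 0.20. The documents do not support that conclusion. The values of *b* have no source, the arithmetic mainly reflects the leniency of a one-patient rule, and it ignores the injection and biodistribution conditions in 7.2. Whether a known metastasis takes up a first-in-human tracer is a legitimate question about a location. Requiring unprompted calls could also produce a false no-go.

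**Cohort A is small and descriptive.** True, and it keeps the point modest. A descriptive estimate can still be biased.

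**Conclusion.** The point holds for the Cohort A sensitivity endpoint. The plan allows one physician to call PET positivity while knowing the reference lesion map, and nothing in it prevents this. Any bias from this source is expected to be upward. Its size cannot be estimated from the documents; the table only shows how it would scale, and the share of uncalled lesions reaching the cut-off caps it. The conclusion rests on an omission: the text neither requires nor forbids a read with staging open.

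The point does not extend to the use of a single reader, to the companion CT or MR, which is needed for localisation, or to the success rule in 7.2. It is a cheap improvement to the reading procedure.

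**What to change.** In 7.1, specify a two-step read by the same physician.

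1. Read the PET with its companion CT or MR only, without the staging scans or report. Record and lock each positive focus and its site.
2. Open the staging scans, match lesions, and record SUVmax for reference lesions not called in step 1.

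In 7.7.2, compute Cohort A lesion-level sensitivity from the locked step 1 calls, and report staging-informed detection from step 2 as secondary. Leave the 7.2 success rule based on location, and report alongside it whether the qualifying uptake was also called in step 1.

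The cost is protocol wording, a lock field on the read form and slightly longer reading time; no extra scan or reader is needed. The sensitivity figure may come out lower. Some prompting will remain, because larger metastases may be visible on the companion scan. The change has to be in place before the Cohort A images are read for the endpoint, since that reader cannot later be made unaware of the staging result.
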